8.3.2 Margin Positivity and SLN Positivity Prediction Analysis

Margin positivity as determined by LS301 and CVG will be tabulated with the gold standard histopathological examination results as the table shown below.

		Histopathology results		
		Negative	Positive at CVG identified locations	Positive at other unidentified locations
CVG results	Negative	n_{11}	0	n_{13}
	Positive at CVG identified locations	n_{21}	n_{22}	0

Diagnostic test operating characteristics including sensitivity, specificity, overall accuracy, positive and negative predictive value will be calculated. The true positives ($=n_{22}$) are the tumors which show positive margins at any location agreed by both the histopathology examination and by LS301 and CVG. Specificity is defined as the proportion of tumors with histopathologically confirmed negative margins which are called to have negative margins by LS301 and CVG, calculated as $n_{11}/(n_{11}+ n_{21})$. Sensitivity is defined as the proportion of tumors which are predicted to have positive margins by LS301 and CVG among the tumors with histopathologically confirmed positive margins both at CVG identified locations and at other locations unidentified by CVG, calculated as $n_{22}/(n_{13}+n_{22})$. Overall accuracy is defined as the proportion of tumors with margin positivity/negativity correctly predicted by the CVG among all tumors, calculated as $(n_{11}+ n_{22})/(n_{11}+n_{13}+ n_{21}+n_{22})$. Positive predictive value is defined as the proportion of tumors with margins called positive at LS301 and CVG identified locations by the histopathology examination among all those predicted to have positive margins by CVG, calculated as $n_{22}/(n_{21}+n_{22})$. Negative predictive value was defined as the proportion of tumors with truly negative margins among those predicted so by CVG, calculated as $n_{11}/(n_{11}+ n_{13})$. The margin positivity rate based on LS301 and CVG will be estimated as $n_{13}/(n_{11}+n_{13}+ n_{21}+n_{22})$. All the estimates will be accompanied with 95% confidence interval. Margin positivity rate will be compared against the current 15.5% margin positivity rate using the two-sided one-sample binomial exact test. Given enough DCIS and invasive breast cancer (IBC), similar diagnostic characteristics will be calculated separately in the subset tumors of DCIS and IBC.

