5.2.4 Intraoperative Review

The operating surgeon will conduct breast cancer surgery as usual without using a device to visualize LS301 fluorescence. To prevent bias in data acquisition, a non-operating member of the study team will wear the CVG before the start of surgery to examine the breast tissue and axillary LNs non-invasively and at the completion of the surgery to examine the excised tissue, SLNs and surgical cavity. Findings with the study will be recorded but will not change the standard of care. The operating surgeon will remain blinded to the fluorescence images throughout the operation. The examining surgical team member will wear the CVG and image all six anatomical aspects (superior, inferior, anterior, posterior, medial and lateral) of the surgical specimen as well as the surgical cavity for LS301 fluorescence. The SPY system will be used for confirmatory fluorescence imaging and compared with CVG detection of LS301 fluorescence, during phase 2 of the study.

Detection of LS301 fluorescence at the cut edge of the excised specimen will determine margin positivity and presence of fluorescence in the SLNs indicate presence of metastatic cancer cells. Given that CVG can detect LS301 fluorescence in tumors several millimeters deep, investigators will use pathology data to initially train the system by correlating fluorescence intensity to background ratio with pathologist's margin assessment. The information will then be used in phase 2 to predict margin positivity in the OR. The detection of fluorescence on excised tissue without correlative fluorescence in the tumor cavity after lumpectomy will predict

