8.0 STATISTICAL CONSIDERATIONS

8.1 Study Design

A rolling six design which is intended for relatively safe trials and shortening the study duration is proposed for the phase 1 portion ⁷⁴. In the rolling six design, three to six patients can be enrolled to a dose each time. The dose de-escalation occurs when two or more DLT occur at a dose level while dose escalation occurs when 3/3, 4/4, 5/5, 5/6 or 6/6 patients are evaluated without DLT ⁷⁵. Three dose levels will be tested in the phase 1 study, 0.05, 0.075 and 0.10 mg/kg. LS301 will be administered intravenously at a starting dose of 0.05 mg/kg to a cohort of six patients and escalate/de-escalate following the decision rule of the rolling six design. Once six patients have been included at the current dose level, inclusions are suspended until at least five of the six patients have completed the procedure without DLT observed in the evaluation period. MTD is hit where two or more patients out of six at a dose level experience DLT. We do not expect any serious adverse events related to LS301 at the initial Dose Level 1. Once the MTD is determined, an expansion cohort with 9 patients will be tested at the MTD and an optimal imaging dose will be recommended for the subsequent phase 2 trial.

At the completion of the expansion cohort, a single arm phase 2 trial will be performed at the optimal imaging dose. A breast surgeon will perform breast conserving surgery per standard of care. At the completion of the surgery, a second investigator (to reduce bias in data collection) will wear the cancer vision goggle (CVG) to visualize the excised tissue to determine if there are any positive margins based on the presence of LS301 fluorescence. If any positive margins are observed, the subject will be considered to have a positive margin; otherwise, the margin is considered negative. The excised tissue will later be examined by a breast cancer pathologist. Standard pathologic techniques will be used to determine if there are positive margins. Particular attention will be paid to the sites marked following CVG assessment to confirm whether the margin is positive or negative at any of these sites, or positive at other locations not identified by CVG. No interventions will be allowed based on the CVG results.

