8.2.2 Endpoint for Prediction of Positive Margin and Positive SLN Analysis

The primary objective is to assess margin status called by LS301 and CVG in comparison to the gold standard histopathological results. The histopathological results of margin positivity has the following possible results: margin negative, margin positive at LS301 and CVG identified locations, margin positive at LS301 and CVG unidentified locations. Using LS301 and CVG, the exercised tissue will be considered to be margin positive and have ink marked at the identified locations if any positive margins are observed; otherwise, the margin is considered negative. Diagnostic test characteristics (sensitivity and specificity) of LS301 and CVG for margin positivity by histology will be established and margin positivity rate, defined as the proportion of tumors with histopathologically confirmed positive margins but missed by CVG, will be estimated. The secondary endpoint of the phase 2 trial is toxicity.

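### The missed-margin rate n13/N in section 8.3.2 leaves out tumours in which CVG finds one positive margin and misses another, so it can only be understated

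*Combined protocol and SAP*

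**What the plan says.** Section 8.1 makes the CVG call once per subject: any positive margin makes the subject positive. Pathology then checks the sites CVG marked and also whether the margin is positive elsewhere ("or positive at other locations not identified by CVG"). Section 5.2.4 has the examiner "image all six anatomical aspects (superior, inferior, anterior, posterior, medial and lateral) of the surgical specimen", so several locations per tumour are in view.

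Section 8.2.2 lists three histology results: "margin negative, margin positive at LS301 and CVG identified locations, margin positive at LS301 and CVG unidentified locations". It describes the margin positivity rate as "defined as the proportion of tumors with histopathologically confirmed positive margins but missed by CVG, will be estimated".

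Section 8.3.2 cross-tabulates CVG against these three results. The true positives n22 "are the tumors which show positive margins at any location agreed by both the histopathology examination and by LS301 and CVG". In the CVG-positive row, the column headed "Positive at other unidentified locations" is fixed at 0, so n13 holds only CVG-negative tumours. Sensitivity is n22/(n13+n22). The margin positivity rate is n13/(n11+n13+n21+n22), compared with 15.5% by an exact binomial test.

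Neither section says how to classify a tumour that is positive at both a marked and an unmarked site, and no location-level analysis is planned.

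**The concern.** The two positive histology results are not mutually exclusive. A tumour can be positive at a site CVG marked and also at a site it did not mark. The any-location rule sends such a mixed tumour to n22, and the fixed zero leaves it nowhere else to go. It then adds nothing to n13/N, although it has a histologically positive margin that CVG did not find.

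Section 8.4 treats the margin positivity rate as the recall rate and powers a comparison of 15.5% with 5%. The 15.5% figure counts a tumour if any margin is positive; section 8.4 expects 14 such tumours among 88. The CVG rate counts a tumour only if CVG called it entirely negative. The two sides of the comparison are therefore not defined alike, and the difference favours CVG. About 14 tumours carry the information, so reclassifying a few of them moves the estimate visibly.

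**Working it through.** **Inputs.** N=88, 14 expected positive-margin tumours, comparator 15.5%, alternative 5%, sensitivity 0.95 against 0.70 (section 8.4); cell definitions and formulas (section 8.3.2). The share of positive tumours with more than one positive location is not given, nor is the correlation of detection between locations. Both are assumed below.

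**The plan's own figures, reproduced by exact one-sided binomial calculation.**
- Sensitivity, pass if at least 13/14: alpha 0.0475, power 0.847. The plan states 0.0475 and 84.7%.
- Margin rate, reject 15.5% if at most 7/88: alpha 0.028, power at 5% 0.9266. The plan states 92.66%.

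The arithmetic is right. The question is which tumours the numerator counts.

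**Worked count, with no model.** Take n22=13 and n13=1.
- As planned: 1/88 = 1.1%.
- If 4 of the 13 also have a missed positive margin: (1+4)/88 = 5/88 = 5.7%. Complete detection is 9/14 = 64.3%, against 13/14 = 92.9% by the any-location rule.
- The plan reports 1.1% and 92.9% in both situations.

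**Size under a simple model.** Let q be the per-location sensitivity and f the share of positive tumours with two positive locations (the rest have one), with independent detection.
- Any-location sensitivity A = (1−f)q + f[1−(1−q)²]
- Complete-detection sensitivity C = (1−f)q + fq²
- Recorded rate = 0.155(1−A); any-missed rate = 0.155(1−C)

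| q | f | A | C | Recorded | Any missed |
|---|---|---|---|---|---|
| 0.70 | 10% | 0.721 | 0.679 | 4.3% | 5.0% |
| 0.70 | 30% | 0.763 | 0.637 | 3.7% | 5.6% |
| 0.70 | 50% | 0.805 | 0.595 | 3.0% | 6.3% |
| 0.95 | 10% | 0.955 | 0.945 | 0.7% | 0.8% |
| 0.95 | 30% | 0.964 | 0.936 | 0.6% | 1.0% |
| 0.95 | 50% | 0.974 | 0.926 | 0.4% | 1.1% |

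**Correlation.** With q=0.70, f=30% and correlation ρ between the two locations, the recorded and any-missed rates are 3.7% and 5.6% at ρ=0, 4.2% and 5.1% at ρ=0.5, and 4.5% and 4.8% at ρ=0.8. At ρ=1 they are equal.

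**Effect on the planned test.** At q=0.70, ρ=0 and f=30-50%, the chance of at most 7/88 is 0.98-0.99 at the recorded rates and 0.81-0.88 when mixed tumours count as missed. At q=0.95 it is practically 1 either way.

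**The case against.** The best defence is that the plan works at tumour level throughout. Section 2.1 asks whether the agent predicts the presence of positive margins, and section 8.1 makes one call per subject. On that footing any-location agreement is a sound definition of sensitivity. It is even stricter than a plain yes/no match, because the location must agree. Specificity conditions on histology-negative tumours, so false marks on positive tumours do not distort it. This part stands: a reader might infer that the planned sensitivity and specificity are themselves biased, and the documents do not support that.

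A reader might also infer that the type I error is inflated. With per-location sensitivity 0.70 and 30-50% of positive tumours having two positive locations, the chance of at least 13/14 is 12-21%, against 4.75%. But 0.70 in section 8.4 is a tumour-level null. In that scenario tumour-level sensitivity is 0.763-0.805, so the null is false and 12-21% is power. At a tumour-level 0.70 the error rate is 0.0475, as stated.

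The size is also open. It rests on an assumed share of multi-margin tumours and on independence, although all locations share one patient, dose and reader. The 5% figure is the alternative used for power, not the test boundary; in the worked count, 5/88 still lies within the 7/88 cut-off.

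Finally, section 8.2.2 could be read as counting only tumours missed altogether, which would match the formula. That reading leaves the mismatch with 15.5% in place, because a tumour with one missed positive margin is still margin-positive. Pathology may well allow mixed tumours to be identified later, but that does not change the formula as written.

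**Conclusion.** The point holds for the margin positivity rate. As defined in section 8.3.2 it omits every tumour with one found and one missed positive margin. That does not fit a rate of positive margins missed by CVG, and it is not like for like with the 15.5% comparator. The direction is certain whenever such a tumour occurs, and the bias is zero if none does.

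The documents do not fix the size. Under independence and a 10-50% share of tumours with two positive locations, the understatement is about 0.7 to 3.3 percentage points at per-location sensitivity 0.70 and about 0.1 to 0.7 points at 0.95. It shrinks to nothing as detection at different locations becomes fully correlated. The planned test against 15.5% would often still reject; the estimate is what is most affected, and it could fall on the other side of 5%. The conclusion does not extend to the type I error of the sensitivity test or to the planned sensitivity and specificity as tumour-level measures.

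**What to change.** Before phase 2 data are seen, amend sections 8.2.2 and 8.3.2:

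1. Split n22 into n22a (every histology-positive location was marked by CVG) and n22b (at least one was marked and at least one missed).
2. Define the margin positivity rate as (n13+n22b)/N.
3. Report complete-detection sensitivity n22a/(n13+n22) beside the planned any-location sensitivity, which stays as the powered tumour-level measure.
4. Use the same table repair to give a category to tumours where CVG marks only wrong sites and histology is positive elsewhere; these now also fall in the fixed zero cell.
5. State in section 8.4 that the 5% behind the 92.66% power refers to the stricter rate, and revisit it if it was meant for n13/N.
6. Confirm that the case report form records each histologically positive site as marked or unmarked. Section 8.1 implies this but does not spell it out. An aspect-level analysis, clustered by patient, is optional and only possible if histology is recorded by the same six aspects, which the documents do not say.

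The cost is SAP wording, one extra table and a check of the form. The reported missed-margin rate may look less favourable.

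### The Section 8.3.2 table sets a possible outcome (CVG marks one site, histology positive only at another) to zero, so four formulas omit tumours that their own definitions include

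*Combined protocol and SAP*

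**What the plan says.** Section 5.2.4 has six aspects of each specimen imaged. Section 8.1 makes the CVG call per subject: "If any positive margins are observed, the subject will be considered to have a positive margin". It then directs pathology to the marked sites "to confirm whether the margin is positive or negative at any of these sites, or positive at other locations not identified by CVG". Section 8.2.2 lists "margin positive at LS301 and CVG unidentified locations" as one of three histology results and does not limit it to CVG-negative tumours.

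Section 8.3.2 cross-tabulates CVG (negative, positive) against these three histology results. The CVG-negative row reads n11, 0, n13; the CVG-positive row reads n21, n22, 0. The definitions that use these cells are:

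- True positives (n22) are tumours that "show positive margins at any location agreed by both the histopathology examination and by LS301 and CVG".
- Sensitivity is taken "among the tumors with histopathologically confirmed positive margins both at CVG identified locations and at other locations unidentified by CVG, calculated as $n_{22}/(n_{13}+n_{22", that is, n22/(n13+n22).
- PPV is taken "among all those predicted to have positive margins by CVG, calculated as $n_{22}/(n_{21}+n_{22", that is, n22/(n21+n22).
- Overall accuracy is the proportion with "margin positivity/negativity correctly predicted by the CVG among all tumors", computed as (n11+n22)/(n11+n13+n21+n22).
- The margin positivity rate is described in Section 8.2.2 as "the proportion of tumors with histopathologically confirmed positive margins but missed by CVG" and computed in Section 8.3.2 as n13/(n11+n13+n21+n22).

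**The concern.** The two printed zeros are not alike. A CVG-negative tumour has no marked location, so it cannot be histology-positive at one; that zero is structural. A CVG-positive tumour can be negative where it was marked and positive somewhere else, and Section 8.1 tells pathology to look for exactly that. The second zero is therefore an assumption about the data.

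If such a tumour occurs, the formulas no longer compute what the text says they compute. Under the location-agreed definition, leaving it out can only raise sensitivity, PPV and accuracy and lower the missed rate. The distortion grows as sensitivity worsens, which is where an optimistic estimate does most harm. With no scoring rule written down, the choice could also be made after the data are seen.

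**Working it through.** **1. Where can the tumour go?** Take a tumour that CVG marks at one site, with histology negative there and positive at another.

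| Cell | Requires | Fits? |
|---|---|---|
| n11 | CVG negative, histology negative | No, on both counts |
| n13 | CVG negative | No, CVG is positive |
| n21 | Histology negative | No, histology is positive |
| n22 | An agreed location | No, none is agreed |
| CVG positive, positive elsewhere | | Yes, but printed as 0 |

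Call this last cell n23. It is histology-positive, CVG-positive and one of the tumours, so the wording of all four measures includes it and all four printed denominators omit it. Specificity and NPV are unaffected, because n23 is neither histology-negative nor CVG-negative.

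**2. The plan's own figures (Section 8.4).** With 88 patients and 15.5% positive, 88 × 0.155 = 13.64, hence 14 histology-positive tumours. The exact one-sided test of 0.70 rejects at 13 or more of 14: level 0.0475, power at 0.95 of 0.847. Both match the plan, and both keep all 14 tumours in the denominator.

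**3. Size of the effect.** Let s be the location-agreed sensitivity and f the share of missed tumours that carry a wrong-place mark. The documents give no value for f; 0.05 to 0.30 is assumed. Per histology-positive tumour, the probability of n23 is w = (1−s)f. Then:

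- expected n23 = 14w
- P(at least one) = 1 − (1−w)^14
- apparent sensitivity = s / [s + (1−s)(1−f)]

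The last two columns come from exact multinomial enumeration with n23 dropped and the critical value recomputed for the tumours that remain.

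| f | Expected n23, s=0.95 / 0.70 | P(n23≥1), s=0.95 / 0.70 | Apparent sensitivity, s=0.95 / 0.70 | Power at 0.95 | Type I error at 0.70 |
|---|---|---|---|---|---|
| 0 | 0 / 0 | 0 / 0 | 0.950 / 0.700 | 0.847 | 0.0475 |
| 0.05 | 0.035 / 0.21 | 0.034 / 0.191 | 0.952 / 0.711 | 0.8473 | 0.0478 |
| 0.10 | 0.07 / 0.42 | 0.068 / 0.347 | 0.955 / 0.722 | 0.8483 | 0.0488 |
| 0.20 | 0.14 / 0.84 | 0.131 / 0.580 | 0.960 / 0.745 | 0.8521 | 0.0540 |
| 0.30 | 0.21 / 1.26 | 0.191 / 0.733 | 0.964 / 0.769 | 0.8588 | 0.0653 |

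With n23 kept in the denominator as not detected, level and power stay at 0.0475 and 0.847 for every f.

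**4. A worked example.** Assume n11=70 and n21=4 (74 histology-negative tumours at about 0.95 specificity; 74 × 0.05 = 3.7), n22=10, n13=3, n23=1. Here f = 1/4, and expected n23 at s=0.70 is 14 × 0.30 × 0.25 = 1.05.

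| Measure | As printed | n23 scored as not detected |
|---|---|---|
| Sensitivity | 10/13 = 76.9% | 10/14 = 71.4% |
| PPV | 10/14 = 71.4% | 10/15 = 66.7% |
| Accuracy | 80/87 = 92.0% | 80/88 = 90.9% |
| Missed rate | 3/87 = 3.4% | 4/88 = 4.5% |

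If any mark counted as detection, sensitivity would be 11/14 = 78.6%. The two-sided exact test of the missed rate against 15.5% gives p=0.00056 as printed and p=0.0028 with n23 counted, so its conclusion is the same.

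**5. Cases where the sensitivity decision turns on the scoring** (one-sided exact test against 0.70):

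- n22=12, n13=1, n23=1: printed 12/13, p=0.064, fails; agreed-location 12/14, p=0.161, fails; any-mark 13/14, p=0.0475, passes.
- n22=12, n13=0, n23=2: printed 12/12, p=0.014, passes; agreed-location 12/14, p=0.161, fails.

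**The case against.** The strongest reply is that this hardly ever matters. Dropping n23 and keeping it as a miss lead to different sensitivity decisions only when n13=0 and n23 is between 2 and 5. Over the assumed range of f, that has probability 0.0003 to 0.012 at sensitivity 0.95 and 0.0003 to 0.018 at 0.70. At design sensitivity, the chance that n23 is 0 and the printed formulas are numerically right is 81% to 97%. The type I error of 0.065 is the top of the range. The worked example uses f=0.25 while its own false-mark rate in histology-negative tumours is 4/74 = 5.4%; at that rate, expected n23 at sensitivity 0.70 would be 14 × 0.30 × 0.054 = 0.23. The sensitivity test also appears only in Section 8.4, whereas Section 8.3.2 plans estimates with confidence intervals. All of this stands, and it limits the size of the problem.

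A second reply is that the plan merely lacks a classification rule, since the Section 8.6 efficacy set keeps such a patient in the analysis. That sharpens the contradiction: the patient is in the set, the table has no cell for the result, and the formulas leave it out.

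A third is that scoring n23 as missed is itself a choice, because the sensitivity wording could be read as crediting any mark. That is true, but the printed sensitivity formula omits n23 under either reading, and the true-positive definition points to the agreed-location one. What counts as an agreed location is also undefined, but n22 already depends on it; the correction does not create that gap.

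**Conclusion.** The concern holds. The table rules out an outcome that Sections 5.2.4, 8.1 and 8.2.2 allow, and four of the Section 8.3.2 formulas do not match their own definitions. The expected numerical effect is small at design performance (apparent sensitivity at most 0.964 against a true 0.95) and moderate if sensitivity is poor (up to 0.769 against 0.70). These sizes rest on the assumed f of 0.05 to 0.30 and on 14 histology-positive tumours; if no such tumour occurs, the printed formulas give the right numbers. The mismatch between table and text does not depend on f. It should be corrected before phase 2, but it does not threaten the design.

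**What to change.** Replace the second 0 in the table with n23 and, following the plan's own definition of a true positive, score it as not detected:

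- Sensitivity = n22/(n13+n22+n23)
- PPV = n22/(n21+n22+n23)
- Accuracy = (n11+n22)/(n11+n13+n21+n22+n23)
- Missed rate = (n13+n23)/(n11+n13+n21+n22+n23)

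Add one sentence stating that a CVG-positive, histology-positive tumour with no agreed location counts as missed. Specificity and NPV stay as printed.

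The cost is one table cell, four formulas and one sentence, with no extra patients, reader or pathology step. Sensitivity, PPV and accuracy may come out slightly lower and the missed rate slightly higher. The Section 8.4 sensitivity figures (0.0475 and 84.7%) stand unchanged. Section 5.2.2 already provides for protocol revision before phase 2, so the rule can be fixed before any phase 2 data exist.

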8.4 Sample Size

The sample size for the phase 1 part will depend on the observed DLT at each dose levels. The phase 1 expansion cohort will use 9 evaluable patients. The table below provides the probability of observing DLT in $\geq 33\%$ in 9 patients based on the binomial distribution. If the true DLT rate is as low as 5%, such a probability is small, only 0.0084 but if the true DLT is 50%, such a probability is very high at 0.91.

True DLT	probability of observed DLT $\geq 33\%$ in 9 patients
1%	0.000084
5%	0.0084
10%	0.053
20%	0.262
30%	0.537
40%	0.768
50%	0.91

The sample size for the phase 2 portion of the study was determined using the following calculations. A total of 88 (14 are expected to have positive margins after standard breast surgery) simultaneously achieves 84.7% power to detect an expected sensitivity of 0.95 against an unacceptable sensitivity of 0.7 and 100% power to detect an expected specificity 0.95 against an unfavorable specificity of 0.7 using a one-sided binomial test. The target significance level is 0.05. The actual significance level achieved by the test on sensitivity is 0.0475 and achieved by the test on specificity is 0.041. The current recall rate (i.e., margin positivity rate) after the use of cavity shave margin is ~19% ³⁶, which agrees with the best practices in Washington University, ~15.5%. 88 patients allows 92.66% power to test a reduction in positive margin rate from 15.5% to 5% based on a one-sided Binomial exact test at a 5% level.

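### The phase 2 margin positivity test compares positives missed by the goggles with the 15.5% surgical positive-margin rate, so a device at the plan's own unacceptable sensitivity usually shows a significant reduction

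*Combined protocol and SAP*

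**What the plan says.** Section 8.2.2 gives the definition: "margin positivity rate, defined as the proportion of tumors with histopathologically confirmed positive margins but missed by CVG, will be estimated". Section 8.3.2 supplies the estimator. After "The margin positivity rate based on LS301 and CVG will be estimated as" comes n13/(n11+n13+n21+n22), where n13 counts tumours called negative by CVG but positive on histology. The test follows: "Margin positivity rate will be compared against the current 15.5% margin positivity rate using the two-sided one-sample binomial exact test".

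Section 8.4 shows where the comparator comes from. It says "The current recall rate (i.e., margin positivity rate) after the use of cavity shave margin is ~19"%, "which agrees with the best practices in Washington University, ~15.5"%. The power statement reads "88 patients allows 92.66% power to test a reduction in positive margin rate from 15.5% to 5"%, using a one-sided exact test at the 5% level. The same section sizes one-sided tests of sensitivity and specificity, each 0.95 against 0.70, on this basis: "A total of 88 (14 are expected to have positive margins after standard breast surgery").

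Section 8.1 adds: "No interventions will be allowed based on the CVG results". Section 5.2.4 keeps the operating surgeon blinded to the fluorescence images, and 1.10 says the images will not alter the surgical plan.

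**The concern.** The two sides of the test measure different things. The 15.5% counts every patient whose margin is positive on histology. The tested rate counts only those whom CVG also missed. It is a false-negative fraction over all tumours, and it falls below the positive-margin rate as soon as CVG detects any positive margin.

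A significant result would naturally be read as positive margins falling from 15.5% to about 5%, which is close to the hypothesis in 1.11. The design cannot show that, because nothing CVG reports may change the excision. The same data could also yield a significant reduction together with a failed sensitivity test, and the plan does not say which governs. In 8.3.2 the comparison with 15.5% is the only hypothesis test named.

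**Working it through.** **Inputs.** N = 88; null rate 0.155; alternative 0.05; sensitivity 0.70 unacceptable and 0.95 expected; 14 expected positives (88 × 0.155 = 13.64); target level 0.05. All are from 8.4. The estimator n13/N is from 8.3.2. Assumptions: one tumour per patient, independent patients, and a 5% level for the two-sided test, which 8.3.2 does not state.

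**Step 1: reproduce the plan's figures.** With X ~ Binomial(88, 0.155), P(X ≤ 7) = 0.0280 and P(X ≤ 8) = 0.0582, so the one-sided test rejects at X ≤ 7. Power is P(X ≤ 7 | 0.05) = 0.9266, matching the stated 92.66%. The sensitivity rule of at least 13 of 14 has level 0.0475 and power 0.847. The specificity rule of at least 59 of 74 has level 0.041 and power of about 1. Both match 8.4.

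The two-sided test in 8.3.2 rejects downwards at X ≤ 6 (p = 0.026; X = 7 gives p = 0.054). Its power at 5% is 0.849, not 0.9266.

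**Step 2: express the tested rate through sensitivity.**

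Expected n13/N = prevalence × (1 − sensitivity).

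- It equals 0.155 at prevalence 0.155 only if sensitivity = 0.
- It equals 0.05 if sensitivity = 1 − 0.05/0.155 = 0.677, below 0.70.
- At sensitivity 0.70 it is 0.155 × 0.30 = 0.0465, already under the 5% target.

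**Step 3: probability of a significant reduction at 15.5% prevalence**, n13 ~ Binomial(88, 0.155 × (1 − sensitivity)):

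| True sensitivity | Missed rate | Two-sided (n13 ≤ 6) | One-sided (n13 ≤ 7) | Sensitivity test (≥ 13 of 14) |
|---|---|---|---|---|
| 0.50 | 7.75% | 0.472 | 0.627 | 0.0009 |
| 0.60 | 6.20% | 0.696 | 0.821 | 0.0081 |
| 0.70 | 4.65% | 0.885 | 0.948 | 0.0475 |
| 0.80 | 3.10% | 0.980 | 0.994 | 0.198 |

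If exactly 14 positives occur, as the last column assumes, the figures for sensitivity 0.70 are 0.907 and 0.969. At sensitivity 0.70 and 15.5% prevalence, the chance of a significant reduction together with a failed sensitivity test is about 0.86 (two-sided) or 0.92 (one-sided).

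**Step 4: vary the prevalence at sensitivity 0.70.**

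| Prevalence | Two-sided | One-sided |
|---|---|---|
| 10% | 0.983 | 0.995 |
| 19% | 0.764 | 0.871 |
| 20% | 0.724 | 0.842 |
| 25% | 0.507 | 0.661 |
| 30% | 0.312 | 0.458 |

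At 10% prevalence, a device with sensitivity zero would still be significant with probability 0.211 (two-sided) or 0.336 (one-sided). The result therefore also depends on whether an external rate suits these patients.

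**Step 5: an example.** There are 14 positive margins; CVG finds 8 and misses 6. Sensitivity is 8/14 = 57%. The missed rate is 6/88 = 6.8%, and the test in 8.3.2 gives p = 0.026 for a reduction.

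**Step 6: false positives.** Neither n21 nor specificity enters the numerator. A reader who flagged every site on every specimen would have n13 = 0 and a significant result.

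**The case against.** The best defence is that n13/N is the positive-margin rate that would remain if every margin flagged by CVG were cleared. That fits the hypothesis in 1.11, makes 15.5% a natural reference, and makes a null of zero sensitivity simply the statement of no reduction. The documents do not state this assumption, however, and the trial does not observe any clearance. Granting it still leaves a test that a 0.70 device meets with probability 0.885 or more at the design prevalence.

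Second, the plan does not make this test a success criterion. Sensitivity and specificity are reported with confidence intervals and sized in 8.4, where a device that flags everything would fail on specificity. This stands and limits the harm, but those tests are absent from 8.3.2 and no rule says which result governs.

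Third, the size depends on prevalence. At sensitivity 0.70 the two-sided probability is close to one half at 25% and 0.31 at 30%, and 1.11 speaks of more than 20%. This stands too, but 15.5% is the value on which the plan is built. It is also true that the two tests have different nulls, so opposite results would not be a logical contradiction, only a confusing report.

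Finally, no participant's care is affected, the formula is disclosed, and phase 2 follows an FDA review at which the protocol may be revised. That makes correction easy; it does not make the comparison valid.

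**Conclusion.** The concern holds, and the comparison is wrong as written. The tested rate and its reference have different numerators, and the reduction that 8.4 powers can neither occur nor be measured in this trial. At the plan's own N = 88 and 15.5% prevalence, a device with the unacceptable sensitivity of 0.70 is declared a significant reduction with probability 0.885 (two-sided) or 0.948 (one-sided), against 0.0475 under the plan's sensitivity test. These figures rest on independent tumours, one per patient, and a 5% level. The size weakens at higher prevalence, but the mismatch does not depend on prevalence.

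Two lesser points follow. Sections 8.3.2 and 8.4 disagree on sidedness, so the stated power does not belong to the stated test. The 15.5% is also a Washington University figure, while 4.0 places phase 2 at UT Southwestern. The main conclusion needs neither.

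**What to change.** 1. In 8.2.2 and 8.3.2, rename n13/N the missed-positive-margin rate and report it descriptively with its 95% confidence interval.
2. Beside it, report the histologic positive-margin rate in the same patients, (n13+n22)/N, in place of the external 15.5%.
3. Delete the test against 15.5% from 8.3.2 and the 92.66% power sentence from 8.4. This also removes the sidedness conflict.
4. Write into 8.3.2 the one-sided exact tests of sensitivity and specificity against 0.70 that 8.4 sizes, and base the phase 2 conclusion on them. Apply each test to the number of positive and negative specimens actually observed, since the 13-of-14 rule fits only 14 positives. With 13 positives all 13 would have to be found, and power at 0.95 falls to 0.513.
5. If the sponsor wants to show what might remain after clearing flagged margins, label it a hypothetical projection, state the assumption that every flagged margin is successfully cleared, and attach no test.

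The cost is wording in three sections, with no added patients or data. The sponsor gives up a claim of reduction that the design cannot support.
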